#### • Revised Opioid Risk Tool (ORT):

The ORT is a self-reported measure used to ascertain a participant's current and future risk of aberrant drug-related behaviors in patients prescribed opioid therapy. Recently a shortened revised ORT was recently developed and will be used in this study. Across 9-items, this tool assesses family history of substance abuse, personal history of substance abuse, age range, and current psychological disease. Each endorsement is scored as 1 for a total score ranging from 0 to 9. Scores of 3 or greater are predictive of high risk for opioid use disorder.

#### • Short Form 36 Health Survey Questionnaire (SF-36):

The SF-36 is a measure of health status and is commonly used in health economics as a variable in the quality-adjusted life year calculation to determine the cost-effectiveness of a health treatment. Including this measure will enable us to capture changes in quality of life over time as it is correlated to the intervention.

#### • Pain Management Questionnaire (PMQ):

The risk of opioid misuse is assessed. The PMQ is a 26-item questionnaire where responses are given on a 5-point Likert scale where 0 = disagree and 4 = agree. Total scores range from 0 to 104, where higher scores indicate increased risk of opioid misuse.

#### • Prescription Drug Use Questionnaire (PDUQ):

The risk of drug misuse is assessed, by collecting longitudinal data on prescription drug use during the study period.

#### • PTSD screener:

This screener is a 5-item screening tool used to assess previous exposure to traumatic events and subsequent presence of the DSM-V diagnostic criteria for PTSD. Each item respondents report "Yes" to can be scored as a point so that a minimum of 3 points is used in primary care settings to be considered probable PTSD.

#### • PROMIS:

Sleep Disturbance, Physical Function, Pain Interference, Prescription Pain Medication Misuse: The PROMIS Sleep Disturbance examines respondent's global severity of insomnia, sleep disruption, and sleep quality over the past seven days. This PROMIS scale is more sensitive at detecting sleep problems than historical measures, such as the Pittsburgh Sleep Quality Index. 42 Again, each of the 4 Likert scale items' raw score are converted to t-scores, ranging from 0 to 100. Like all PROMIS measures, t-scores are normed to the US population, with a mean of 50 and standard deviation of 10.43 Lower scores indicate better sleep. PROMIS Physical Function measures participants' selfreported capability to conduct physical activity. This includes capturing function in upper extremities and lower extremities (walking or mobility) as well as a respondent's ability to conduct activities of daily living. There are 4-items on the short form questionnaire and respondents report their capabilities to perform each task on a Likert scale from 5, "without any difficulty", to 1, "unable to do". All 4-items' saw scores are summed before being transformed into t-scores ranging from 0 to 100. Higher scores are better and indicate greater physical function. The validated instrument is comparable to numerous legacy measures often used across diverse patient populations.  The PROMIS Pain Interference scale assesses the extent to which pain impedes engagement with social, cognitive, emotional, physical, and recreational activities over the past 7 days. Pain interference is an essential aspect of pain management to capture in order to better understand how pain impacts the activities of individuals rather than subjective severity alone.  On each of the scale's 4-items respondents choose how much pain impeded a specific function or activity, ranging from 1, "not at all", to 5, "very much". Scores are summed across all items and transformed to a t-score ranging from 0 to 100, with lower t-scores indicate less interference due to pain. The PROMIS Pain Interference scale has been found to be comparable in responsiveness to traditional measures of pain interference used including the Brief Pain Inventory Interference subscale and the 36-Item Short Form Survey (SF-36) Bodily Pain scale. The *PROMIS measure of Prescription Pain* 

*Medication Misuse* assesses current abuse of prescription pain medication, chiefly opioids. The scale has been validated in patient populations with chronic non-cancer pain and has been found to be highly correlated with the Pain Medication Questionnaire (PMQ)."

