#### **Study Procedures/Assessments:**

Potential patients will be identified during the daily orthopaedic trauma morning report. Eligibility will be determined by the clinical research coordinator (CRC).

If the patient meets inclusion criteria, he/she will be approached by the CRC, and if informed consent is obtained, they will be enrolled into RedCAP for randomization into Group 1 (non- LCS) or Group 2 (LCS). After consenting, enrolling, and allocation, research staff will administer a battery of measures on tablets stored in RedCap, or on paper and later transcribed into REDCap to all participants (See Table).

Each day throughout hospitalization, the average pain score over the past 24-hours will be recorded via the nursing staff. During their follow up visits with the surgical team at Grady Hospital scheduled at 2-weeks, 6-weeks, and 3-months postoperatively participants will again be provided a tablet to complete outcome measures. In the event participants cannot physically travel to the clinic, appointments will be conducted over video conferencing and participants will have the option to be emailed the outcome measures to complete. If they are unable to complete the measures via email within 72-hours study staff will call participants to complete measures over the phone. If no response, paper copies of the measures will be mailed to participants with prepaid postage to return them.

The following data will be collected on the patients:

- Demographics:
  - Name, date of birth, date of admission, gender, ethnicity, body mass index.
- Trauma registry data:
  - Data abstraction that is completed by a separate quality team contained within the trauma department. i.e., injury severity score, mechanism, drug screen on arrival, alcohol screen, pre-existing conditions, inpatient complications.
- Comprehensive social determinants of health (SDOH) survey:
  - Includes assessments of: housing, financial stability, education, community context, intimate partner violence, health literacy, prior personal and family substance use, a validated measure of post-traumatic stress disorder, adverse childhood experiences, and mental illness. This has been utilized in prior research by this team and takes approximately 20-25 minutes to complete (attached).

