#### VISIT SCHEDULE AND ASSESSMENTS

Assessment	Visit 1:	Visit 2:	Visit 3:	Visit 4:
	Inpatient	2 Weeks (±	6 Weeks (±	3 Months (±
	Hospitalization	7 days)	14 days)	14 days)
Demographics	X			
Trauma registry data	X			
Comprehensive Social Determinants of Health (SDOH) Survey	X			
Revised Opioid Risk Tool (ORT)	X			
Short Form 36 Health Survey Questionnaire (SF-36)	X			X
Pain Management Questionnaire (PMQ)	X	X	X	X
Prescription Drug Use Questionnaire (PDUQ)	X	X	X	X
PTSD Screener	X			X
PROMIS: Sleep Disturbance	X	X	X	X
PROMIS: Physical Function	X	X	X	X
PROMIS: Pain Interference	X	X	X	X
PROMIS: Prescription Pain				X
Medication Misuse				
Opioid Literacy Tool (OLT)	X			X
Patient Satisfaction Survey		X		
Naloxone Questionnaire		X	X	X
PAC-SYM	X	X	X	
Inpatient Opioid Utilization (MME/day)	X			
Inpatient Numerical Rating Scale (NRS) Pain Score	X	X	X	X
Medication Electronic Monitoring (MEMS) devices:		X	X	X
Defense and Veterans Pain Rating Scale (DVPRS)	X	X	X	X

Inpatient Sleep Actigraphy	X				l
Field notes and participant quotes	X	X	X	X	l
Participant Compensation	X	X		X	ı

Questionnaires/surveys and meetings with the Life Care Specialist will occur during scheduled telehealth appointments. No charges will be generated specifically relating to the research components.

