#### **Eligibility Criteria:**

The inclusion criteria are:

- Male and female patients 18 years of age or older
- Orthopaedic trauma patients with an isolated injury requiring surgery
- Informed consent obtained
- Working cellphone

The exclusion criteria are:

- Enrolled in a study that does not permit co-enrollment
- Unlikely to comply with the follow-up schedule
- Unable to converse, read or write English at elementary school level
- Unlikely to complete surveys at home, access to phone
- Incarcerated
- Pregnant
- COVID positive

Patients will be free to withdraw from the study at any time, for any reason.

A patient may also be withdrawn/removed by the study team, if necessary, to protect the patient's health. Once a patient withdraws, the reason will be documented.

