#### **Statistical Analysis:**

**Aim 1:** Examine differences in post-surgical patient-reported pain related outcomes between those in the intervention compared to the control arm. A multivariable mixed effects logistic regression model will be constructed to test the hypothesis that participants in the intervention arm have lower average NRS pain scores and PROMIS scores postoperatively compared to participants in the control arm. A separate linear mixed effects model will be constructed for each outcome. This modeling approach will enable the team to examine the mean differences in each patient-reported pain related outcome while adjusting for covariates (e.g., mental health history, BMI, surgery type, etc.).  The mixed effects modeling will account for potential collinearity between participants seen by the same surgeon by fitting a random effect for both factors. Models will be constructed using a Least Absolute Shrinkage and Selection Operator (LASSO) method. 50,51 An extension of traditional ordinary least squares regression model building, LASSO is a machine learning method capable of balancing bias and variance to build the most predictive model with a large subset of covarying factors using a penalized approach. A LASSO approach enables the team to systematically evaluate the variance introduced into regression modeling by hundreds of potential confounders. This unique quantitative capability will allow the research team to exploit the hundreds of data points collected from the electronic health records and the patient-reported outcomes collected per participant. The inclusion of these longitudinal measures makes it feasible to reduce statistical variation in the mixed effects models over time and therefore isolate the effect of the intervention. The fit of the most appropriate and still parsimonious model produced by the LASSO will be assessed based on the AIC score.

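### Visit 1 PROMIS Pain Interference and Sleep Disturbance can mix time before and after injury, and Aim 1 does not keep that visit apart from the postoperative outcomes

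*Combined protocol and SAP*

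**What the plan says.** **Recall period.** The PROMIS entry under Study Procedures/Assessments says Pain Interference rates the extent to which "pain impedes engagement with social, cognitive, emotional, physical, and recreational activities over the past 7 days". Sleep Disturbance covers "global severity of insomnia, sleep disruption, and sleep quality over the past seven days". No such period is stated for Physical Function, so the point is limited to these two scales.

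**Schedule.** In Visit Schedule and Assessments, the rows "PROMIS: Pain Interference" and "PROMIS: Sleep Disturbance" are marked at all four visits. Visits 2 to 4 have day windows. Visit 1 is labelled only as the inpatient stay.

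**Timing of Visit 1.** Study Procedures/Assessments states: "Potential patients will be identified during the daily orthopaedic trauma morning report". It then states: "After consenting, enrolling, and allocation, research staff will administer a battery of measures on tablets stored in RedCap". Neither sentence ties completion to a day after injury or surgery. Eligibility Criteria admits "Orthopaedic trauma patients with an isolated injury requiring surgery" and sets no limit on time since injury. Nowhere is the recall wording changed for Visit 1, and days since injury are not listed among the data to be collected.

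**Analysis.** Aim 1 in Statistical Analysis compares PROMIS scores between arms postoperatively in mixed models, with covariates chosen by LASSO. It does not say whether the Visit 1 score is an outcome, a covariate or neither.

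**The concern.** A week's recall collected a few days after a fracture spans two different states: ordinary life before the injury, and pain and disturbed sleep in hospital. The resulting score is neither a pre-injury baseline nor a post-injury value, and what it measures depends on the day the patient happened to complete it.

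Two things are at stake. If Visit 1 enters the Aim 1 models as one of the repeated outcomes, a measurement of a different kind, taken around the time the intervention starts, is averaged with the follow-up scores and may dilute the arm contrast. If it is used as a baseline, or for change from baseline, part of the variation between patients reflects the day of completion and not the patient. That part cannot be separated afterwards unless the timing was recorded.

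**Working it through.** **The plan's own figures.** No figure in the plan bears on the recall window. The power statement (200 patients, 85%, a 0.5-point difference in mean pain score) gives no SD or within-patient correlation, so it cannot be reproduced, and this point does not depend on it.

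**Inputs.** Recall length is 7 days (PROMIS entry). The days from injury to completion, d, are not given, so a range is shown. Visit windows come from the visit schedule.

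**Step 1: pre-injury share at Visit 1.** If each day in the window counts equally, the share is max(0, 7 − d)/7.

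| d (days after injury) | Calculation | Pre-injury share |
|---|---|---|
| 1 | 6/7 | 86% |
| 2 | 5/7 | 71% |
| 3 | 4/7 | 57% |
| 4 | 3/7 | 43% |
| 5 | 2/7 | 29% |
| 6 | 1/7 | 14% |
| 7 or more | 0/7 | 0% |

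**Step 2: the same check at follow-up.** Visit 2 is at 2 weeks ± 7 days, so the earliest is day 14 − 7 = 7 after surgery. Its recall week reaches back to the day of surgery, which cannot precede the injury, so the pre-injury share is 0%. Visits 3 and 4 are later still. The mixing is confined to Visit 1.

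**Step 3: how much noise this could add (illustration).** Assume a T-score of 50 before injury and 70 after it. The expected Visit 1 score is 50 × share + 70 × (1 − share):
- day 1: 50 × 0.857 + 70 × 0.143 = 52.9
- day 3: 50 × 0.571 + 70 × 0.429 = 58.6
- day 5: 50 × 0.286 + 70 × 0.714 = 64.3
- day 7: 70.0

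If d is spread evenly over days 1 to 7, the number of pre-injury days is uniform on 0 to 6. Its SD is √((7² − 1)/12) = 2, so the share has SD 2/7 = 0.286. Completion day alone then adds an SD of 0.286 × 10 = 2.9 T-points for an assumed gap of 10, or 0.286 × 20 = 5.7 for a gap of 20. The PROMIS entry gives a population SD of 10. The gaps and the even spread are assumptions, not figures from the plan.

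**The case against.** **The outcome set may already be Visits 2 to 4.** Study Procedures/Assessments uses the word postoperatively for the 2-week, 6-week and 3-month visits, so Aim 1 most naturally refers to those. The sentence "The inclusion of these longitudinal measures makes it feasible to reduce statistical variation in the mixed effects models over time" belongs to the discussion of covariates and variance; it does not announce that Visit 1 will be pooled. This stands: the text is ambiguous and does not state a pooling plan. But some Visit 1 forms may be completed after surgery, and nothing excludes them.

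**A fixed loss of effect.** A reader might infer that the recall week makes the plan understate a constant follow-up effect by a quarter, because one visit in four would carry no arm effect (1 − 3/4 = 25%). The documents do not support this. Any early visit without an arm effect would do the same under any recall wording. The figure also needs equal visit weights, a constant later effect and no arm-by-visit term, none of which Aim 1 states.

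**A poorer covariate.** A reader might also infer that a mixed score predicts later scores less well than a pre-injury score would. Nothing in the documents shows this. A score that captures some acute post-injury pain could predict better.

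**Unknown timing.** That many patients answer within days of injury is inferred from inpatient recruitment of trauma patients. Patients may also give recent days more weight. Both limits stand, which is why Step 1 is only a range.

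**No bias between arms.** Randomisation should balance completion day on average. This stands.

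**Conclusion.** The point holds as a minor one. As scheduled, these two Visit 1 scores can contain anything from 86% pre-injury time (day 1) to none (day 7 onward), while follow-up scores contain none. Visit 1 is therefore not comparable with Visits 2 to 4 on the same scale, and Aim 1 should say that it is not one of the outcomes. The size rests on equal weighting of days and on a completion time that the documents do not give; patients who complete Visit 1 on day 7 or later are unaffected. What follows is a problem of interpretation, noise and possible dilution. It should not be read as a bias between arms or as a fixed percentage loss of effect.

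**What to change.** In Statistical Analysis, Aim 1:
- Define the PROMIS outcomes as Visits 2 to 4 only, and state that Visit 1 is never pooled with them.
- Keep the Visit 1 score in each model as a baseline covariate whether or not LASSO selects it, provided it was completed before the first LCS contact. The battery is given after allocation, so this condition has to be checked for each patient.
- Include days from injury and days from surgery to Visit 1 completion alongside that covariate.

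In Study Procedures/Assessments and the visit schedule, add those two intervals to the recorded data. The date of admission already collected is only a partial substitute.

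The cost is one or two extra fields and model terms. Anchoring the Visit 1 forms to the week before injury is optional only: it would give a clearer baseline, but it departs from the standard instruction of a normed instrument at one visit and relies on retrospective recall by injured inpatients.

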#### • Opioid Literacy Tool (OLT):

This survey is designed to assess the accuracy of knowledge about opioids (3 questions) and opioid-related risks (5 questions). Accuracy of opioid knowledge responses are given on a dichotomous scale (yes/no) and a pick-N scale, the latter of which will represent a percent accuracy of identified opioids and/or opioid-containing medication. Responses for accuracy of knowledge about opioid-related risks are given on a 7-point scale where 1 = definitely true and 7 = definitely false. For these 5 questions, a total score ranges from 5 to 35 and higher scores indicate improved literacy (accurate understanding of prescription opioid addiction-risk, opioid dependance and risk of opioid overdose).

#### • Patient Satisfaction Survey:

Patient satisfaction with received clinical care will be assessed with a modified Press Ganey Integrated Survey. Integrated study-specific questions will align with the conventional rating scale of "strongly agree" – "strongly disagree". This survey will capture a comprehensive picture of each participant's care experience. Higher scores indicate higher satisfaction and will be compared among study arms and to the Hospital Consumer Assessment of Healthcare Providers and Systems (HCAHPS) comparative feedback database.

#### • Naloxone Questionnaire:

Each participant will complete a Naloxone questionnaire evaluating knowledge and details of utilization, if applicable.

#### • Inpatient Pain and Opioid utilization:

Inpatient utilization will be extracted from the electronic health record (EHR) by study staff upon participants' discharge from the hospital. Opioid medication dosage will be transformed to a total universal measure known as morphine milligram equivalent (MME). MME will be averaged over the length-of-stay (LOS) for a daily dosage, known as MME/day. Additionally, the study team will review participants' EHR at each study time point up to 3-months to determine MME throughout postoperative recovery and rehabilitation. *Pain numerical rating scale (NRS):* The NRS requires respondents to rate the intensity of their pain on a defined scale from 0, "no pain", to 10, 'the worst pain imaginable". The NRS is a commonly used pain assessment tool in both clinical practice and research.  However, the NRS is a single static measure of pain and does not capture the biopsychosocial presentations of pain including physical functioning. As such a battery of objective (e.g. actigraphy) and patient-reported outcomes are needed to best ascertain patient participants' pain experiences. Inpatient NRS, which is recorded by the clinical care team throughout each day, will be extracted from the electronic health record (EHR) by study staff upon participants' discharge from the hospital.

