CWC proposes to introduce a Life Care Specialist (LCS) as an integral member of the clinical team, with a focus on "pain coaching" for trauma patients. In an analogous role served by CCLS in pediatrics, the LCS will introduce orthopaedic trauma patients to non-pharmacologic coping strategies for pain. Further, they will provide much needed patient-centric education on individualized risk for opioid misuse, as well as overdose prevention and safe disposal of unused opioids.

CWC's primary focus is to introduce a behavior-specific intervention at the time of inpatient hospitalization for trauma to decrease overall opioid utilization and improve pain control in the post-trauma time period. We are collaborating with key stakeholders in the opioid epidemic to develop an official pain management protocol, as well as conducting an introductory study for a new field of Pain Management. The goal is to see Life Care Specialists (LCS) staffed in hospitals to focus on pain management and addiction prevention for patients. The LCS position does not currently exist in the healthcare field. The LCS is a behavior-based pain "coach" who educates patients on risks of opioid dependence and offers non-traditional non-pharmacologic options for pain control. In addition, the LCS will act as a liaison between the patient and

the physician – to ensure that traditional pharmacologic-based pain control regimens are optimized. Current post-operative protocols for pain management in trauma are very opioid-based. They lack multimodal non-opioid based pharmacologic options and they have no non-pharmacologic behavioral-based component.

All LCS involved in the research study will become certified as a teacher of the Community Resiliency Model (CRM). CRM is an evidence-based model of wellbeing created by Elaine Miller-Karas of the Trauma Resource Institute.

LCS Role and Responsibilities will be overseen by CWC:

- The LCS will provide patients with individualized risk assessment for opioid misuse.
- LCS will act as patient's "Pain Coach." Providing targeted education and behavior-based pain treatment options.
- LCS will train and provide CWC evidence based non-pharmaceutical pain management techniques, using the Community Resiliency Model.
- The LCS will use the Opioid Risk Tool (ORT) as the method to identity the risk of substance misuse.
- LCS will provide education, support and resources.

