#### • Discharge data:

Inpatient morphine equivalents (24 hours prior to discharge), average pain score (24 hours prior to discharge), discharge pain medications prescribed, discharge morphine equivalents prescribed, hospital length of stay and discharge disposition.

- Actigraphy based sleep and activity data (e.g. average hours of sleep, average daily steps): Study participants will be provided with a wrist actigraphy device to wear during their hospitalization and throughout their recovery until their 2-week follow up appointment with the surgical team. Participants will return their actigraphy devices at the 2-week follow up appointment or be provided a pre-paid envelope to take home and mail back the device after the visit. Wrist actigraphy is a valid and objective tool to measure activity patterns and sleep-related parameters, which has been used in patient populations with both acute and chronic pain. Actigraphy data includes objective quantitative measures of sleep, such as total sleep time, sleep latency, fragmentation, wake after sleep onset, and sleep efficiency. Additionally, activity level is also captured using wrist actigraphy, including total activity time, steps, physical activity intensity, and total energy expenditure. Participants will receive, and be trained on how to wear, a screen-less actigraphy device on their wrist (GT3XP-BTLE, Actigraph, LLC, USA). Devices will be set to record in 30-second epochs at a medium sensitivity level for scoring sleep and wake time. Wear time validation will be accomplished using the Choi algorithm, as it more accurately estimates time worn accounting for forward and backward motions. The sleep data will be computed using the Cole-Kripke algorithm, which accurately distinguishes sleep from wakefulness approximately 88% of the time. Metabolic equivalent of tasks and energy expenditure will be measured with the Freedson algorithms. By uniquely pairing actigraphy data with PROMIS patient-reported pain, sleep, and physical function measures, this study will be one of the first to provide a robust analysis of sleep quality and activity in tandem to pain presentations in adult surgical patient populations during hospitalization and throughout immediate post-discharge recovery following surgery. These research efforts adhere to recommended best practices for using actigraphy to examine health outcomes.35

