Aim 2: Evaluate the effectiveness of Life Care Specialist intervention on reducing long-term postoperative opioid medication utilization. As described above, a systematic machine learning guided model construction approach will be used to also test the working hypothesis that participants in the intervention will report decreased utilization of opioid pain medications both in the inpatient and outpatient setting up to 3-months postoperatively. Separate mixed-effects models will be constructed to estimate differences in average MME/day during inpatient hospitalization as well as to estimate difference in average MME/day over every study follow up point up to 3-months postoperatively.

Aim 3: Explore the feasibility of utilizing actigraphy devices to capture postoperative functional outcomes among patients during their hospitalization and up to 2-weeks postoperatively following orthopaedic trauma. Generalized estimating equations (GEE) will be used to explore changes in functional outcomes over the 2-

week postoperative period. For example, activity will be measured as average step per day and sleep will be measured as average nightly sleep efficiency and duration. Separate GEE will be computed for each actigraphy related measure. In the event a significant change in any of the objective outcomes, a linear mixed-effect model will be constructed to ascertain any significant differences in actigraphy collected outcomes exist between participants in the intervention and the control arms over the two-week postoperative period.

Power: A sample of 200 provides 85% power ( $\alpha$ =0.05) to detect a difference as small as 0.5 in the mean pain score between the intervention arm and the controls using repeated measures mixed effects modeling (Power Analysis and Sample Size Software, NCSS, Kaysville, UT, USA). All analyses will be conducted in R (R Core Team, Vienna, Austria) by the Co-PI and his team at the Nell Hodgson Woodruff School of Nursing ([name]). The *glmnet* package will be used to determine which variables should be included in the regression models using a LASSO approach, the *lme4* package will be employed to compute final regressions and assess fit. Post hoc power analyses will be conducted when exploring differences in outcomes based on demographics (e.g., gender).

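### Aim 2's inpatient MME/day is averaged over the whole stay, so it counts doses given before randomisation and understates a real daily effect

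*Combined protocol and SAP*

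**What the plan says.** The section Inpatient Pain and Opioid utilization takes inpatient doses from the EHR at discharge, converts them to morphine milligram equivalents and states: "MME will be averaged over the length-of-stay (LOS) for a daily dosage, known as MME/day". Statistical Analysis, Aim 2, compares that quantity between arms: "Separate mixed-effects models will be constructed to estimate differences in average MME/day during inpatient hospitalization".

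Study Procedures/Assessments gives the order of events: "Potential patients will be identified during the daily orthopaedic trauma morning report"; the coordinator then checks eligibility and approaches the patient, and "if informed consent is obtained, they will be enrolled into RedCAP for randomization". The Introduction describes the purpose as to "introduce a behavior-specific intervention at the time of inpatient hospitalization for trauma". Allocation therefore falls inside the stay.

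No section starts the MME window at randomisation, gives the expected time from admission to randomisation, or says whether randomisation comes before or after surgery. The Discharge data section collects "hospital length of stay and discharge disposition" but gives no expected stay.

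On adjustment, Aim 1 describes drawing covariates from "the hundreds of data points collected from the electronic health records", and Aim 2 adopts the same approach. The Power paragraph says that glmnet will be used to "determine which variables should be included in the regression models using a LASSO approach". MME before randomisation is not named as a covariate and is not forced in.

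**The concern.** An outcome that compares randomised arms should count what happens after allocation. Here the pre-allocation doses sit in the numerator and the pre-allocation days in the denominator. They cannot respond to the intervention, so they pull the arm difference towards zero. This pilot is also meant to supply effect sizes, so an understated reduction would carry into the planning of a later trial.

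A second issue follows from dividing by length of stay. Stay is observed after randomisation. If it differed between arms, the two averages would cover different stretches of recovery, and part of any difference in MME/day would reflect which days were averaged.

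**Working it through.** **Inputs.** From the documents: the outcome definition, the order of events, and 200 patients with 100 allocated to LCS. The only power figure is 85% for a 0.5 difference in mean pain score. It comes without an SD or correlation, so it cannot be reproduced, and it does not concern MME. None is given for MME/day; 85% serves below only as a reference level. Assumed, because the documents give none of them: k, L, the day-to-day correlation r (0.3 to 0.7, equal variance each day), and every dose value.

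**1. Dilution with equal stays.** Stay average = [k × (pre-randomisation mean) + (L − k) × (post-randomisation mean)] / L. Only the second term can respond, so the expected difference is the true difference × (L − k)/L, a loss of k/L.

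| k (days) | L = 3 | L = 5 | L = 7 |
|---|---|---|---|
| 0.25 | 8% | 5% | 4% |
| 0.5 | 17% | 10% | 7% |
| 1 | 33% | 20% | 14% |

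**2. Power, unadjusted.** Var(stay) = r + (1 − r)/L and Var(post) = r + (1 − r)/(L − k). The number of patients analysed from randomisation that would carry the same information is n = 200 × ((L − k)/L)² × Var(post)/Var(stay). Power = Φ((1.960 + 1.036) × √(n/200) − 1.960).

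- L = 5, k = 1, r = 0.5: 200 × 0.64 × 0.625/0.600 = 133, so 85% becomes 69%.
- L = 5, k = 0.25, r = 0.5: n = 182, so 85% becomes 82%.
- For r = 0.3 to 0.7 and L = 3, 5, 7: k = 0.25 gives 79–80%, 81–82%, 82–83%; k = 1 gives 54–60%, 68–70%, 73–75%.

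**3. Power, adjusted.** With k and L the same for every patient, the stay average given the pre-randomisation mean is the post-randomisation mean multiplied by (L − k)/L, plus a known term. The t statistic is therefore identical for the two windows. A simulation (k = 1, L = 5, r = 0.5, true effect −0.30 SD, 4,000 runs) gave:

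- Unadjusted: stay average −0.239 (SE 0.110, power 58%); from randomisation −0.299 (SE 0.112, power 76%).
- Adjusted for pre-randomisation MME: 92.8% power for both windows, with the stay-average estimate still −0.239.

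The covariate supplies the power, and the window corrects the size of the estimate.

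**4. Stays that differ by arm.** Assume no effect, one pre-randomisation day, and daily use of 90, 70, 60, 50, 45, 40 in both arms, with a control stay of 5 days.

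| LCS stay | Whole-stay difference | Randomisation-to-discharge difference |
|---|---|---|
| 4 days | 270/4 − 315/5 = +4.5 | 180/3 − 225/4 = +3.75 |
| 6 days | 355/6 − 315/5 = −3.83 | 265/5 − 225/4 = −3.25 |

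The bias runs either way. Dropping the pre-randomisation day removes (4.5 − 3.75)/4.5 = 17% of it in the first row and (3.83 − 3.25)/3.83 = 15% in the second.

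Simulation agrees (100 per arm, no effect, 80 MME on one pre-randomisation day, day SD 30, r = 0.5, mean later days 4 in control and 3 in LCS):

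- Flat 40 MME/day after randomisation: the stay average is off by +2.3 MME/day and rejects in 10.6% of runs, or 18.1% when adjusted for pre-randomisation MME. From randomisation the figures are +0.04 and 5.6%.
- Use starting at 60 and falling 20% a day: the stay average is off by +5.0 and rejects in 28–29%. From randomisation it is still off by +4.3 and rejects in 22%.

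A common window removes this. On that falling profile the first two post-randomisation days average (60 + 48)/2 = 54.0 in both arms, whereas a four-day mean is 44.3.

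**The case against.** The strongest reply is that the size is unknown and may be slight. Daily screening at the morning report is compatible with early enrolment; at k = 0.25 and L of 5 to 7 the dilution is 4% to 5% and reference power falls only to 81–83%. That stands.

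A reader might infer that the trial stands to lose a large part of its power, as in the 54–60% figure. The documents do not support that. The figure needs a full pre-randomisation day in a three-day stay and no adjustment for pre-randomisation MME, whereas the plan specifies covariate-adjusted models. What remains is that this covariate is left to selection.

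A reader might also infer that the LCS will change length of stay and so distort the comparison, or that pre-allocation doses are the main source of such distortion. No section says or implies an effect on stay; the components are education, coping techniques and referral. A full-day difference is a chosen scenario: at half a day (4 v 3.5 later days, flat profile) the unadjusted stay average rejected in 6.3% of runs. Where stay does differ, step 4 shows that most of the bias comes from tapering.

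Finally, a reader might infer that outpatient MME has no source, since the Aim 2 paragraph names none. Inpatient Pain and Opioid utilization assigns it to EHR review at each time point to 3 months.

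**Conclusion.** The defect holds: the inpatient Aim 2 outcome includes doses given before allocation, and nothing in the plan restarts the window. With equal stays and a constant daily effect, the estimate is understated by k/L: 4% to 33% over the assumed k of 0.25 to 1 and L of 3 to 7, and negligible if randomisation follows admission closely. Loss of power is confined to an analysis without pre-randomisation MME. With that covariate and fixed k and L, the test keeps its power and only the effect size shrinks, but LASSO selection does not guarantee the covariate.

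The bias from unequal stays is conditional on an arm difference in stay. It can go either way, comes partly from pre-randomisation days and mainly from tapering, and is not cured by a plain randomisation-to-discharge mean. The true size of either effect cannot be fixed from the documents.

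**What to change.** - Start the inpatient MME window at randomisation.
- Either model MME per day with a term for day since randomisation, or use a fixed post-randomisation window whose length is stated in advance, together with how days after an early discharge are handled.
- Force pre-randomisation MME per day into the model, outside the LASSO selection.
- Record the time from admission to randomisation, so that the pre-allocation share of the stay can be reported.

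The cost is abstraction of time-stamped doses from the EHR, which is already the source, in place of a single average, plus revised analysis wording. Patients discharged early contribute fewer days. No extra patients or visits are needed.

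A minor clarification can be made in the same revision: state how EHR review and the MEMS caps each feed outpatient MME/day, and reconcile this with the Objectives section, which promises the amounts patients actually used.
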